## **3.5 COST AND COMPENSATION**

### **3.5.1 Costs**

NIH does not bill health insurance companies or participants for any research or related clinical care that participants receive at the NIH Clinical Center. If some tests and procedures are performed outside the NIH Clinical Center, participants may have to pay for these costs if they are not covered by their insurance company. Medicines that are not part of the study treatment will not be provided or paid for by the NIH Clinical Center.

### **3.5.2 Compensation**

Participants will not be compensated on this study.

### **3.5.3 Reimbursement**

The NCI will cover the costs of some expenses associated with protocol participation. Some of these costs may be paid directly by the NIH and some may be reimbursed to the participant/guardian as appropriate. The amount and form of these payments are determined by the NCI Travel and Lodging Reimbursement Policy.

## **3.6 CRITERIA FOR REMOVAL FROM PROTOCOL THERAPY AND OFF STUDY CRITERIA**

Prior to removal from study, effort must be made to have all subjects complete monthly safety visits (+/- 7 days) for 90 days following the last dose of study therapy. These visits will consist of H&P and labs (including renal, liver, complete blood count + platelets, coagulation studies). Patients will revert to standard of care once coming off study. If clinically indicated, patients may continue to be followed by phone or clinic visits beyond that time and up to a year at the NIH/NCI or their local urologist.

### **3.6.1 Criteria for Removal from Protocol Therapy**

Subjects are free to withdraw from further treatment or to withdraw consent to participate in this study at any time and without prejudice to further treatment. For subjects who withdraw their consent for study participation, no further study specific assessments will be performed and no additional study data will be collected. For subjects who withdraw from further treatment only will remain on study for further evaluations but receive no additional study treatment. The investigator may also withdraw a subject from study treatment or from the study if he or she deems it to be in the best interest of the subject or if the subject is unable to comply with the study. All subjects withdrawing only from further treatment should have enter the Post-Treatment Period and have the appropriate assessments performed 90 days after the last dose of study drug, unless the subject withdraws consent for the procedures. If clinically indicated, patients may continue to be followed by phone or clinic visits beyond that time and up to a year at the NIH/NCI or their local urologist. The reasons and details relevant to subject withdrawal must be recorded in the source documents and in the CRFs.

In addition, an individual subject will not receive any further investigational product if any of the following occur in the subject in question:

- Completion of protocol therapy

- Unacceptable toxicity as defined in section [3.3](#) and [Appendix C](#)
- Adverse event that, in the opinion of the investigator, contraindicates further dosing of either study drug
- Subject experiences a DLT during the DLT evaluation period (see section [3.1.1](#))
- Requirement for prohibited medications/therapies
- Subject met eligibility criteria at screening but then subsequently is determined to have met one or more of the exclusion criteria for study participation and continuing investigational therapy might constitute a safety risk
- Subjects refuses to use contraception as required by the protocol
- Disease progression (as defined in section [6.2.4.3](#)) or confirmation that the subject is no longer benefiting from study treatment
- Grade 2 or greater hyperbilirubinemia
- Participant requests to be withdrawn from active therapy
- Unacceptable Toxicity as defined as any serious adverse event that is unexpected relative to the known safety profile of the investigational agents in the opinion of the investigator
- Sponsor or Manufacturer terminates the study
- The FDA requests that the sponsor terminate treatment of a specific subject or subjects or all subjects
- Subject noncompliance that, in the opinion of the investigator or sponsor, warrants withdrawal; e.g. refusal to adhere to scheduled visits
- Investigator discretion
- Positive pregnancy test or intent to become pregnant or intent to breast-feed or is breastfeeding
- Disease recurrence with high-grade bladder cancer

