##### **3.1.1 Dose Limiting Toxicity (DLT)**

A DLT will be defined as any Grade 3 or higher toxicity that occurs during the initial 6-week period the subject is on treatment (i.e., the DLT evaluation period). Toxicity that is clearly and directly related to the primary disease or to another etiology is excluded from this definition. Since this trial also involves immunotherapy, immune-related AEs (irAEs) are defined as AEs of an immune nature (i.e. inflammatory) in the absence of a clear alternative etiology. In the absence of a clinically significant abnormality, repeat laboratory testing will be conducted to confirm significant laboratory findings prior to designation as a DLT. The following will be DLTs:

- Inability to reduce prednisone dose below 10 mg within 6 weeks (rather than 12 weeks) due to ongoing immune-related adverse reaction of Grade >1
- Any Grade 4 irAE not attributed to local tumor response (e.g., inflammatory reaction attributed to local tumor response or inflammatory reaction at sites of metastatic disease or lymph nodes)
- Any  $\geq$  Grade 3 colitis
- Any Grade encephalopathy
- Any  $\geq$  Grade 3 neurotoxicity
- Any  $\geq$  Grade 3 peripheral neuromotor syndromes
- Any Grade 2 or higher noninfectious pneumonitis irrespective of duration
- Any Grade 3 irAE, excluding colitis that does not downgrade to Grade 2 within 3 days after onset of the event despite optimal medical management including systemic corticosteroids or does not downgrade to  $\leq$  Grade 1 or baseline within 14 days

- Total bilirubin  $>1.5 - 3.0 \times$  ULN (Grade 2 Hyperbilirubinemia)
- ALT or AST  $>8 \times$  ULN
- ALT or AST  $>5 \times$  ULN for more than 2 weeks
- ALT or AST  $>3 \times$  ULN and
- ALT or AST  $>3 \times$  ULN and INR  $>1.5$
- ALT or AST  $>3 \times$  ULN with appearance of fatigue, nausea, vomiting, right upper quadrant pain or tenderness, fever, rash, and/or eosinophilia ( $>5\%$ )
- Any Grade  $\geq 3$  non-irAE toxicity that does not downgrade to Grade  $\leq 1$  or baseline status (for patients who entered the study with an existing laboratory abnormality) within 14 days
- Inability to receive  $\geq 75\%$  or more of scheduled study treatment (both Vicineum and durvalumab) during the first six weeks of the trial

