### 3.3 DOSE MODIFICATIONS

#### 3.3.1 Durvalumab

Following any biopsy or TURBT, study drug must be interrupted for a maximum of 2 weeks before restarting Durvalumab treatment.

For adverse events (AEs) that are considered at least partly due to administration of durvalumab outside of the DLT evaluation period, the following dose adjustment guidance may be applied:

- Treat each of the toxicities with maximum supportive care (including holding the agent suspected of causing the toxicity where required).
- If the symptoms promptly resolve with supportive care, consideration should be given to resuming the same dose of durvalumab along with appropriate continuing supportive care.
- If medically appropriate, dose modifications are permitted for durvalumab. All dose modifications should be documented with clear reasoning and documentation of the approach taken (see [Appendix C](#)).

In addition, there are certain circumstances in which durvalumab should be permanently discontinued (see [Appendix C](#)). In circumstances where subjects cannot tolerate durvalumab or do not meet retreatment criteria to receive either drug, subjects will be taken off protocol therapy.

Following the first dose of durvalumab, subsequent administration of durvalumab can be modified based on toxicities observed (see [Appendix C](#)).

Based on the mechanism of action of durvalumab leading to T-cell activation and proliferation, there is the possibility of observing immune related Adverse Events (irAEs) during the conduct of this study. Potential irAEs include immune-mediated enterocolitis, dermatitis, hepatitis, and endocrinopathies. Subjects should be monitored for signs and symptoms of irAEs. In the absence of an alternate etiology (e.g., infection or PD) signs or symptoms of enterocolitis, dermatitis, hepatitis, and endocrinopathy should be considered to be immune-related.

Dose modification recommendations and toxicity management guidelines for immune-mediated reactions, for infusion-related reactions, and for non-immune-mediated reactions are detailed in [Appendix C](#).

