- Vicineum dosing must be held for any subject whose AST or ALT doubles from their baseline value and is  $\geq 2 \times$  ULN; OR for a bilirubin  $\geq 2 \text{ mg/dl}$  ( $\geq 34 \text{ } \mu\text{mol/L}$ ). However, if Grade 2 hyperbilirubinemia occurs during the DLT evaluation period, then a DLT is present and treatment will be permanently discontinued and patient will be removed from study. The investigator should evaluate subjects for the etiology of any changes in these values. Vicineum treatment may be resumed upon improvement or stabilization of AST and ALT of  $\leq 2 \times$  baseline or  $\leq 2 \times$  ULN; OR for a bilirubin  $\leq 2 \text{ mg/dl}$  ( $\leq 34 \text{ } \mu\text{mol/L}$ ) provided that Grade 2 hyperbilirubinemia did not occur.
- The investigator should consider holding Vicineum treatment for patients with a clinically significant UTI requiring antibiotic therapy until improvement. Investigators should also consider holding Vicineum treatment for patients with grade II hematuria.

Missed doses should not be made up. In the Maintenance Phase, dosing should be restarted as soon as there is AE resolution i.e., treatment should not be postponed longer in order to align with the initial every-other-week schedule.

If study treatment is postponed longer than 3 weeks, the investigator should consider whether the subject should remain on treatment.

In circumstances where subjects cannot tolerate Vicineum or do not meet retreatment criteria to receive either drug, subjects will be taken off protocol therapy.

The reasons and details relevant to the subject postponement and/or discontinuation of study treatment must be recorded on the CRF. The Investigator must notify Sesen Biotherapeutics if study treatment is discontinued.

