### **16.3 APPENDIX C: DURVALUMAB DOSING MODIFICATION AND TOXICITY MANAGEMENT GUIDELINES**

These guidelines are standardized for durvalumab trials. However, these guidelines are superseded and should be superceded by any protocol-specific DLTs as as specified in section 3.1.1. This is specifically the case for toxicities such as hyperbilirubinemia, encephalopathy, neurotoxicity, peripheral neuromotor syndromes, and transaminase elevation as well as others.

---

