
Hepatitis
 
Infliximab should not be used for management of immune-related hepatitis.
 
PLEASE SEE shaded area immediately below this section to find guidance for management of “Hepatitis (elevated LFTS)” in hepatocellular carcinoma (HCC) patients (or secondary tumour involvement of the liver with abnormal baseline values [BLV])
	
Any Grade
 
(Refer to NCI CTCAE applicable version in study protocol for defining the CTCAE grade/severity)
	
General Guidance
	
For Any Grade
 
 
Patients should be thoroughly evaluated to rule out any alternative etiology (e.g., viral hepatitis, disease progression, concomitant medications).
 
Monitor and evaluate transaminases (aspartate aminotransferase [AST], alanine aminotransferase [ALT], alkaline phosphatase [ALP], and total bilirubin).
 

	
ALT or AST <math>\leq</math> 3 x ULN or total bilirubin <math>\leq</math> 1.5 x ULN
	
 
No dose modifications.
 
If it worsens, then consider holding therapy.
 
	
 
Continue transaminase and total bilirubin monitoring per protocol.
 

	
ALT or AST <math>> 3 \leq 5</math> x ULN or total bilirubin <math>> 1.5 \leq 3</math> x ULN
	
 
Hold study drug/study regimen dose until ALT or AST <math>\leq 3 \times</math> ULN or total bilirubin <math>\leq 1.5 \times</math> ULN. Resume study drug/study regimen after completion of steroid taper (<10 mg prednisone or equivalent).
 
Permanently discontinue study drug/study regimen for any case meeting Hy's law laboratory criteria (AST or ALT <math>\geq 3 \times</math> ULN AND bilirubin <math>\geq 2 \times</math> ULN without initial
 
	
 
Regular and frequent checking of transaminases and total bilirubin (e.g., every 1 to 2 days) until LFT elevations improve or resolve.
 
If no resolution to ALT or AST <math>\leq 3 \times</math> ULN or total bilirubin <math>\leq 1.5 \times</math> ULN in 1 to 2 days,
 

Specific Immune-Mediated Reactions			
Adverse Events	Severity Grade of the Event	Dose Modifications	Toxicity Management

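### After the 6-week DLT period, Grade 2 bilirubin is a permanent stop under Section 3.6.1 but hold-and-resume under Section 3.3.1 and Appendix C, and no text says which governs

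*Combined protocol and SAP*

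**What the plan says.** Section 3.6.1 opens its list of removal criteria by stating that "an individual subject will not receive any further investigational product if any of the following occur". One bullet is "Grade 2 or greater hyperbilirubinemia". It carries no time limit and stands apart from the DLT bullet, "Subject experiences a DLT during the DLT evaluation period". A further bullet removes patients for unacceptable toxicity as set out in Section 3.3 and Appendix C.

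Section 3.1.1 makes total bilirubin above 1.5 and up to 3.0 x ULN a DLT and labels that band "Grade 2 Hyperbilirubinemia". DLTs are confined to the first 6 weeks on treatment.

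Section 3.3.1 says of adverse events at least partly due to durvalumab: "outside of the DLT evaluation period, the following dose adjustment guidance may be applied". That guidance refers to Appendix C. In the Appendix C hepatitis table, the row for total bilirubin above 1.5 and up to 3 x ULN holds treatment until bilirubin is back to 1.5 x ULN or less, and then says "Resume study drug/study regimen after completion of steroid taper". The opening note of Appendix C says "these guidelines are superseded and should be superceded by any protocol-specific DLTs", cites Section 3.1.1, and names hyperbilirubinemia among its examples.

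Section 3.3.2 holds Vicineum at bilirubin of 2 mg/dl or more (a separate AST/ALT criterion also triggers a hold). Its explicit permanent stop for Grade 2 is limited to the DLT period. It allows resumption at 2 mg/dl or less only "provided that Grade 2 hyperbilirubinemia did not occur".

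**The concern.** After week 6, two parts of the protocol give opposite instructions for the same laboratory value. A site following Section 3.6.1 stops both drugs for good. A site following Section 3.3.1 into Appendix C holds and then restarts.

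The primary objective is safety and tolerability. Exposure, treatment discontinuation and the recorded reason for it would depend on which section was read. So would the time over which adverse events are collected, because Section 6.1 runs that collection to 90 days after the last administration. There is also a direct safety side: staff should not have to choose between a stop rule and a restart rule.

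**Working it through.** The documents give no figure for this point, so there is nothing to reproduce. The check compares the rules by period and then compares the two bilirubin scales.

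**1. Inside the DLT period (first 6 weeks).** Grade 2 bilirubin is a DLT (3.1.1). A DLT ends study drug (3.6.1), and 3.3.2 says the same explicitly. The 3.3.1 guidance applies only outside this period, and Appendix C gives way to the 3.1.1 DLTs. The sections agree on treatment and on the DLT count.

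**2. After the DLT period, bilirubin above 1.5 and up to 3 x ULN.**

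| Section | Instruction |
|---|---|
| 3.6.1 | No further investigational product |
| 3.3.1 with Appendix C | Hold, then resume after recovery and steroid taper |
| Appendix C, ALT/AST also raised | Permanent stop if Hy's law laboratory criteria are met, or if ALT/AST is above 3 x ULN with bilirubin above 2 x ULN |
| 3.3.2 (Vicineum) | Hold at 2 mg/dl or more; no resumption once Grade 2 has occurred |

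The conflict is therefore two-way, stop against hold-and-resume. It is clearest for an isolated bilirubin rise. Between 2 and 3 x ULN with raised transaminases, Appendix C can reach the same permanent stop as 3.6.1. Above 3 x ULN, Appendix C stops permanently and agrees with 3.6.1.

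**3. Does the supersession note settle it?** It gives way to DLTs under 3.1.1. A rise after week 6 is not a DLT by that definition. Naming hyperbilirubinemia shows the topic was considered but does not extend the note beyond the DLTs it cites.

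**4. The two scales.** Grade 2 starts above 1.5 x ULN; the 3.3.2 hold starts at 2 mg/dl. They meet at ULN = 2.0 / 1.5 = 1.33 mg/dl. The protocol refers only to the institutional ULN, so a range of 1.0 to 1.5 mg/dl is assumed:

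| ULN (mg/dl) | Grade 2 above (1.5 x ULN) | Grade 2 with no 3.3.2 bilirubin hold | Held under 3.3.2 but not Grade 2 |
|---|---|---|---|
| 1.0 | 1.50 | >1.50 to <2.0 | none |
| 1.2 | 1.80 | >1.80 to <2.0 | none |
| 1.3 | 1.95 | >1.95 to <2.0 | none |
| 1.4 | 2.10 | none | 2.0 to 2.10 |
| 1.5 | 2.25 | none | 2.0 to 2.25 |

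Below 1.33 mg/dl, some Grade 2 values trigger no bilirubin hold in 3.3.2 although 3.6.1 stops treatment. Every value that does trigger the hold is already Grade 2 or worse, so its resumption is barred. At or above 1.33 mg/dl, the resume clause has some use.

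**5. Share of treatment exposed to the conflict.** (52 - 6) / 52 = 46/52 = 88% for the first year; (104 - 6) / 104 = 98/104 = 94% with optional maintenance.

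**6. Patients affected.** No rate of Grade 2 bilirubin after week 6 is given. Purely as illustration, with 24 patients and assumed rates of 1% to 10%, the expected number is 24 x 0.01 = 0.24 to 24 x 0.10 = 2.4. The chance of at least one, 1 - (1 - p)^24, is 21% to 92%. That range is too wide to serve as an estimate.

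**The case against.** The best reply is that the texts differ in force. Section 3.6.1 is mandatory and lists hyperbilirubinemia on its own, apart from both the DLT bullet and the bullet that refers to Appendix C. It reads like a deliberate study-specific rule. Section 3.3.1 is permissive, and Appendix C describes itself as standard across durvalumab trials and as a recommendation. A careful reader could conclude that 3.6.1 governs. This stands in part and lowers the practical risk. It is still an inference: no section states precedence after week 6, and 3.6.1 itself brings in Appendix C for unacceptable toxicity.

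A second reply is that the planned analyses report toxicity grades and DLTs by dose level, and that no discontinuation count is named as an endpoint. That is correct. The effect is on exposure, observation time and the description of tolerability, not on a prespecified test.

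A reader might infer that the conflict distorts DLT counts or the de-escalation decision. The documents do not support this, because the sections agree inside the DLT period. A reader might also see a three-way conflict with 3.3.2 as the third branch. For a Grade 2 event, however, a hold that may not be lifted is in effect a stop of Vicineum, in line with 3.6.1. Finally, entry is allowed up to 1.5 x ULN and the bilirubin DLT starts just above it. That is a design choice and not a contradiction between sections, and 3.1.1 excludes toxicity clearly due to another etiology and provides for repeat testing before a laboratory finding is called a DLT.

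**Conclusion.** The contradiction is real and confined to the time after the DLT period. There, Grade 2 bilirubin without the transaminase elevations that trigger the Appendix C stop is a permanent stop under 3.6.1 and hold-and-resume under 3.3.1 with Appendix C. It can arise in 88% of the planned first year, or 94% of two years. How many patients it would touch cannot be sized from the documents.

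The scale mismatch in 3.3.2 is secondary and depends on the ULN. It takes the form described for an assumed ULN below 1.33 mg/dl. It would go too far to call the resume clause empty in general, or to say the rules disagree for every value between 1.5 and 3 x ULN. The first fails at a higher ULN; the second ignores the Appendix C stop when ALT or AST is also raised.

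This is an inconsistency worth correcting for patient safety and for a clear tolerability record. It does not undermine the run-in or the choice of dose level.

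**What to change.** Reconcile Sections 3.3.1, 3.3.2 and 3.6.1, the opening note of Appendix C and its hepatitis row, so that they give one consistent instruction for Grade 2 bilirubin after the DLT period. State it for each drug and on one scale (x ULN or mg/dl). Say which section takes precedence when the general durvalumab guidance and the study-specific text differ. Which clinical rule is right is for the sponsor and investigator to decide.

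The cost is wording in five places and IRB review of the amendment. No extra tests are needed, because the study calendar already has a hepatic panel every 2 weeks after induction.

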### **3.6.2 Off-Study Criteria**

The following are off study criteria that will preclude further follow-up:

- Completed study follow-up period
- Participant requests to be withdrawn from study
- Death
- Patient is lost to follow-up
- Patient enrolled into another clinical study

### **3.6.3 Lost to Follow-up**

A participant will be considered lost to follow-up if he or she fails to return for 3 scheduled visits and is unable to be contacted by the study site staff.

The following actions must be taken if a participant fails to return to the clinic for a required study visit:

- The site will attempt to contact the participant and reschedule the missed visit and counsel the participant on the importance of maintaining the assigned visit schedule and ascertain if the participant wishes to and/or should continue in the study.
- Before a participant is deemed lost to follow-up, the investigator or designee will make every effort to regain contact with the participant (where possible, 3 telephone calls and, if necessary, an IRB approved certified letter to the participant's last known mailing address or local equivalent methods). These contact attempts should be documented in the participant's medical record or study file.
- Should the participant continue to be unreachable, he or she will be considered to have withdrawn from the study with a primary reason of lost to follow-up.

## **4 CONCOMITANT MEDICATIONS/MEASURES**

### **4.1 PERMITTED CONCOMITANT MEDICATIONS**

Investigators may prescribe concomitant medications or treatments (e.g., acetaminophen, diphenhydramine) deemed necessary to provide adequate prophylactic or supportive care except for those medications identified as “excluded” as listed in Section [4.2](#).

### **4.2 EXCLUDED CONCOMITANT MEDICATIONS**

The following medications are considered exclusionary during the study.

1. Any investigational drugs
2. Any concurrent chemotherapy, radiotherapy (except palliative radiotherapy), immunotherapy, biologic or hormonal therapy, including investigational therapy for cancer treatment. Concurrent use of hormones for noncancer-related conditions (e.g., insulin for diabetes and hormone replacement therapy) is acceptable. Subjects who enter the study with low risk prostate cancer and then progress to require androgen-deprivation therapy (ADT) when already enrolled on this trial may continue on trial as per investigator discretion.
3. Immunosuppressive medications including, but not limited to systemic corticosteroids at doses not exceeding 10 mg/day of prednisone or equivalent, methotrexate, azathioprine, and TNF- $\alpha$  blockers. Use of immunosuppressive medications for the management of investigational product-related AEs or in subjects with contrast allergies is acceptable. In addition, use of inhaled and intranasal corticosteroids is permitted.
4. Live attenuated vaccines within 30 days of durvalumab dosing (i.e., 30 days prior to the first dose, during treatment with durvalumab and for 30 days post discontinuation of durvalumab. Inactivated vaccines, such as the injectable influenza vaccine, are permitted.)

